Many aspects of PCV13 vaccination in adults still need to be answered:

- No efficacy shown for all cause CAP
 - 5% decline in all cause pneumonia consistent but not significant
- No efficacy shown for mortality
- Efficacy unknown for high risk patients
 - Immunocompromised
 - Institutionalized
 - Very old
- Duration of protection at least about 4 years
 - Need for revaccination?
- Real world effectiveness?
 - How can we distinguish direct PCV13 effects from indirect effects?

PPVS23 is still used in many European countries in the elderly, even though its efficacy against IPD and non-invasive pneumonia is controversial. A meta-analysis on PPSV23 efficacy reported a VE of 74% (OR 0.26, 95% CI: 0.15-0.46, $I^2 = 0$) against IPD, 46% (OR 0.54, 95% CI 0.43 to 0.67, $I^2 = 19$ %) against all-cause pneumonia in low-income countries and 29% (OR 0.71, 95% CI 0.45 to 1.12, $I^2 = 93$ %) in high-income countries¹¹. The latest literature overview that estimated PPSV23 effectiveness for preventing vaccine-type IPD in the 65+ years, suggested an average VE of 60% (range 40%-70%)¹². The PPSV23 effectiveness varied according to immune-competency and decreased after 3-5 years.^{13,14}

Pneumo2¹⁵ survey was conducted under SpIDnet project between July-November 2013 among 30 EU/EAA countries to gather information on IPD surveillance, laboratory capacity and vaccination programmes. None of the 22 countries that filled in a PCV13 questionnaire had introduced the vaccination in adults at that time; however the latest data from ECDC show that seven countries recommend PCV13 in adults¹⁶. Among the 24 countries that filled in a PPSV23 questionnaire in 2013 survey, 10 stated PPSV23 was included in the national immunisation plan and three in the regional immunisation plan. In 12 countries it was recommended by professional associations and in 20 countries the vaccine was on the market. The target population for the PPSV23 vaccination were high risk groups for invasive pneumococcal infection (15 countries), elderly ≥65 years of age (six countries) or ≥60 years of age (one country).

¹¹ Moberley S, Holden J, Tatham DP, Andrews RM. Vaccines for preventing pneumococcal infection in adults. Cochrane Database Syst Rev. 2013 Jan 31;1:CD000422. doi: 10.1002/14651858.CD000422.pub3.

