4.3 Study population

The study population comprises the elderly ≥65years eligible for vaccination and living in the catchment area of the laboratory/ hospitals participating in the already set up surveillance system, for whom information is collected for surveillance purposes.

► Each study site to define the study population according to the date of PPSV23/PCV13 introduction (if the case), recommendations for vaccination according to age / high risk groups.

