4.5.1 Case definitions

For the primary outcome, a case is a hospitalised person eligible for PPSV23 and/or PCV13 vaccination confirmed with an IPD according the ECDC case definition (below), in whom serotyping identified a vaccine serotype (PCV13 or PPSV23 IPD/SpCAP cases). The EC 2008 case definition should be used to recruit IPD cases²²:

PNEUMOCOCCAL INVASIVE DISEASE(S) (Streptococcus pneumoniae)

Clinical criteria

Not relevant for surveillance purposes

Laboratory criteria

At least one of the following three:

- Isolation of Streptococcus pneumoniae from a normally sterile site
- Detection of Streptococcus pneumoniae nucleic acid from a normally sterile site
- Detection of Streptococcus pneumoniae antigen from a normally sterile site

Epidemiological criteria

NA

Case classification

A. Possible case

NA

B. Probable case

NA

C. Confirmed case

Any person meeting the laboratory criteria

For secondary outcomes, the case is defined as above for the primary outcome, and in addition:

- A specific vaccine serotype is identified (this can be a vaccine serotype or vaccine related serotype);
- A clinical manifestation is identified as: meningitis, pneumonia, bacteraemia and others;
- Severity is assessed according to: ICU admission and/or length of hospital stay >14 days and/or death within 30 days.

²² European Commission, Commission Decision 2008/426/EC of 28 April 2008 amending Decision 2002/253/EC laying down case definitions for reporting communicable diseases to the Community network under Decision No 2119/98/EC of the European Parliament and of the Council (notified under document number C(2008) 1589)

► Each study site to state the case definitions for each primary and secondary outcome according to data collected.

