4.5.2 Reference group

The primary reference group comprises all persons ≥65 years eligible for vaccination, hospitalised for an IPD/SpCAP laboratory confirmed with a serotype identified as non-vaccine serotype (NVT, mainly nonPPSV23 controls) and excluding vaccine related serotypes. Cases with IPD/SpCAP due to vaccine related serotypes will be excluded from the analysis (i.e. serotypes from the same serogroups as the vaccine serotypes for which cross-protection was demonstrated or assumed).

For the secondary outcomes, the reference groups are the following:

- Specific vaccine serotype/ vaccine—related serotypes: NVT-IPD controls, same as for the primary outcome (see above);
- A [clinical manifestation]: NVT controls of the respective [clinical manifestation];
- Antimicrobial susceptibility: NVT controls in which antimicrobial susceptibility is investigated, and MIC provided (EUCAST thresholds will be taken into account for classification);
- Severe IPD cases: NVT-IPD controls admitted in the ICU / a length of hospital stay >14 days.

Matching

Matching can be an option when clustering by age, time or location is observed or the number of VT-IPD cases overpass NVT-IPD cases. For example, when the vaccine serotype IPD cases are clustered in certain age/location/time and NVT in other ages/locations/time, then matching/group matching by age/location/time would be required. Matching by region (or hospital if possible), age and time of hospitalisation (month/years) can be used²³.

► Each study site to describe the selection of the control group (all NVT controls) and matching by different variables (if it is the case) taking into account the outcome used.

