4.5.4 Cases and controls inclusion and exclusion criteria

IPD/SpCAP cases and controls will be included if individuals are eligible for PCV13 or PPSV23 vaccination, were hospitalised for an IPD or SpCAP, and have had the serotype identified.

IPD cases and controls will be excluded if:

-

²³ Andrews, N., et al. Impact and effectiveness of 23-valent pneumococcal polysaccharide vaccine against invasive pneumococcal disease in the elderly in England and Wales. Vaccine 2012: 30, 6802–6808

- Individuals are not eligible for vaccination due to conditions that contra-indicate vaccination;
- Testing of non-sterile body fluid was used for diagnosis;
- Recurrent invasive disease is diagnosed (only the first episode will be included in the analysis). Recurrent invasive disease is defined as IPD episodes in the same individual with the diagnosis/admission date at 30 days apart or identification of the same serotype.
- Serotyping could not be performed.

SpCAP cases and controls will be excluded if:

- Individuals are not eligible for vaccination due to conditions that contra-indicate vaccination;
- Recurrent disease is diagnosed (only the first episode will be included in the analysis). Recurrent
 disease is defined as SpCAP episodes in the same individual with the diagnosis/admission date at 30
 days apart or identification of the same serotype.
- Serotyping could not be performed.

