Appendix 1: Validation of "non-vaccine serotypes" as control group using other control groups

The use of the indirect cohort method implies that the serotyping results are available for all or a systematic sample of IPD or SpCAP cases. This assumption should be validated by comparing the VE results with those of other controls groups using the same data sources.

Below we present advantages and disadvantages of each additional groups and specific features for analyses.

Using a unique identifier allows linkage of various datasets:

- hospital discharge register diagnosis codes;
- laboratory data;
- vaccination data.

This constitutes the unique opportunity to measure effectiveness using different control groups and evaluate which one better represents the vaccination coverage of the population that gives rise to IPD/SpCAP caused by vaccine serotypes.

These additional control groups could be:

- 1. Hospitalised elderly according to other disease codes:
 - a. hospitalised elderly≥65 years for other ICD codes than pneumococcal related codes as presented in Table 4.
 - b. hospitalised elderly ≥65 years for condition that do not include those considered high risk for IPD/SpCAP (i.e. ICD9CM 800-999 or ICD10CM: S00-T98: Injury and poisoning).

Advantages:

- Feasibility (access to the data)
- Same type of data available
- Can compute VE against all type IPD/SpCAP

Disadvantages:

- Susceptible to selection bias: the control group might not represent in terms of exposure the population given rise to the pneumococcal cases
- Need for adjustment for different confounders: severity of disease, access to care (information not always available)
- 2. Controls from community
 - a. Screening method using the vaccination coverage of the elderly by age and risk groups

Advantages:

- Quick analysis when incidence rates are not available
- Could be done only with data readily available for surveillance or available surveys
- Can be used for other outcomes such as all type IPD/SpCAP
- Adjustment difficult but possible for some factors (age groups, high risk groups) if vaccination coverage is available by group

Disadvantages:

- VC in the population might not represent the one of the source population of pneumococcal hospitalised cases
- VE estimates are highly dependent on time period during which it is used and the choice of outcome (VT versus all type IPD/SpCAP)

Vaccine coverage in the reference group

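### Appendix 1 does not restrict hospital comparators 1a and 1b to vaccine-eligible people, so at risk-group sites their crude VE is biased downward and can make a valid NVT-based VE look too high

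*Protocol*

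**What the plan says.** The main study restricts everyone to people eligible for vaccination:

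- Section 4.3: "The study population comprises the elderly ≥65years eligible for vaccination and living in the catchment area". Each site then sets its population by its own recommendations, which may rest on age or on high-risk group.
- Section 4.5.1: "a case is a hospitalised person eligible for PPSV23 and/or PCV13 vaccination confirmed with an IPD".
- Section 4.5.2: "The primary reference group comprises all persons ≥65 years eligible for vaccination, hospitalised for an IPD/SpCAP laboratory confirmed", with a non-vaccine serotype.
- Section 4.5.4: "IPD/SpCAP cases and controls will be included if individuals are eligible for PCV13 or PPSV23 vaccination". The same sentence also requires admission for IPD or SpCAP.

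Appendix 1 offers further control groups to test whether the NVT controls reflect coverage in the population that produces the vaccine-type (VT) cases. The two hospital groups are:

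- 1a: "hospitalised elderly≥65 years for other ICD codes than pneumococcal related codes as presented in Table 4".
- 1b: "hospitalised elderly ≥65 years for condition that do not include those considered high risk for IPD/SpCAP", with injury and poisoning codes as the example.

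Neither mentions eligibility. For this type of control, Appendix 1 lists possible selection bias on exposure as a disadvantage. It names severity and access to care as confounders to adjust for.

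Section 1.1 shows that risk-group programmes exist. In a 2013 survey, "The target population for the PPSV23 vaccination were high risk groups for invasive pneumococcal infection (15 countries"), while six countries named people aged 65 and over and one named people aged 60 and over.

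**The concern.** A control group for this design has to show the vaccination odds of the population from which the cases come. At a site whose recommendation follows risk group, that population is the at-risk elderly. A person outside the risk groups cannot become a case or an NVT control, but can enter 1a or 1b.

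The eligibility rule in 4.5.4 does not close the gap, because it covers people admitted for IPD or SpCAP and the Appendix 1 comparators are admitted for something else. The wording of the two groups also leans away from eligible people. Group 1b selects admissions for conditions that are not high risk. Group 1a excludes codes by reference to Table 4, but the ICD Table 4 now lists the underlying risk conditions, and the pneumococcal codes are in Table 2. Read literally, 1a drops admissions for the very conditions that confer eligibility at a risk-group site.

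What is at stake is how the validation is read. Replacement (6.1) pushes the NVT-based VE above the truth. Non-eligible comparators push the hospital-control VE below it. Both leave the NVT-based VE the higher of the two, so the crude comparison cannot tell a faulty NVT group from a wrongly composed hospital group.

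**Working it through.** The protocol gives no figure on this point, so there is none to reproduce. The check uses its own measure (5.3): VE = 1 - odds of vaccination in VT cases / odds in controls.

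**Inputs**
- True VE 60%: the average for PPSV23 against vaccine-type IPD cited in 1.1.
- c, coverage in eligible people: assumed 50%, with 30% and 70% as alternatives.
- c0, coverage in non-eligible people: assumed 5%, with 2% and 10% as alternatives.
- s, share of hospital comparators who are eligible: assumed.

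**Formulas**
- Case odds = (1 - 0.60) × c/(1 - c), since all cases are eligible.
- Comparator coverage p = s·c + (1 - s)·c0.
- Crude hospital-control VE = 1 - case odds / [p/(1 - p)].

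**Worked case**, c = 50%, c0 = 5%, s = 70%: case odds = 0.4 × 1 = 0.4; p = 0.35 + 0.015 = 0.365; comparator odds = 0.365/0.635 = 0.575; VE = 1 - 0.4/0.575 = 30.4%.

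**With c0 = 5%**

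| Eligible share s | p, c = 50% | Crude VE, c = 50% | p, c = 30% | Crude VE, c = 30% |
|---|---|---|---|---|
| 70% | 0.365 | 30.4% | 0.225 | 41.0% |
| 50% | 0.275 | -5.5% | 0.175 | 19.2% |
| 40% | 0.230 | -33.9% | 0.150 | 2.9% |

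**Wider range**, c from 30% to 70% and c0 from 2% to 10%: crude VE is 27.8% to 51.2% at s = 80%, -24.7% to 39.2% at s = 60%, and -126.3% to 21.9% at s = 40%.

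**Restriction.** With s = 100%, p = c and the result is 60% at every coverage tried.

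**Stratification**, c = 50%, c0 = 5%, s = 60%. Per 1,000 comparators, 600 are eligible (300 vaccinated, 300 not) and 400 are non-eligible (20 vaccinated, 380 not). Crude: 1 - 0.4/(320/680) = 15.0%. Within the eligible stratum: 1 - 0.4/(300/300) = 60.0%. The non-eligible stratum holds no cases and contributes nothing.

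**Age-based site.** If everyone aged 65 or over is eligible except an assumed 2% who have contraindications and are unvaccinated, then p = 0.98c. VE is 58.8%, 58.4% and 57.3% for c = 30%, 50% and 70%, which is a negligible shift.

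**Comparison with replacement bias.** The formula in 6.1 reproduces its stated 92.5% and 75%. For a true VE of 60%, with 30% effectiveness against carriage and 40% vaccine-type carriage (the values behind the 75%), it gives 1 - 0.4/(1 + 0.3 × 0.4/0.6) = 66.7%, a gap of 6.7 points. Non-eligible comparators at s = 70% alone give 60 - 30.4 = 29.6 points, in the same direction.

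**The case against.** Several objections have force.

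- **No rejection rule.** A reader might infer that a site following Appendix 1 would discard a sound NVT-based result. The text does not support that. The comparison is open, meant to show which group better represents coverage, and the hospital group may equally be the one found wanting. The groups are optional, and each site describes its own validation. This stands.
- **The weakness is disclosed.** Appendix 1 says that hospital controls may misrepresent exposure. This stands in part: the warning is general, and neither eligibility nor risk condition is named for adjustment, although the protocol already controls eligibility for NVT controls.
- **Adjustment would deal with it.** Sections 4.7, 5.4 and 5.5 provide for underlying conditions, and stratifying on eligibility restores 60% above. This stands where the data exist. Appendix 1 does not carry that adjustment over to 1a and 1b. If 1b is read as excluding everyone with a high-risk condition, no eligible comparators remain to stratify on.
- **Section 4.3 already covers everyone.** It can be read that way, but Appendix 1 does not say so and defines its groups independently.
- **The country counts are weak evidence.** One might infer from 15 against seven that most sites are risk-group-only. The survey dates from 2013, concerns countries rather than participating sites, and its categories may overlap. It shows only that such programmes exist.
- **The indirect cohort is itself in doubt there.** Section 6.1 reports, from a study in children, that the method is not recommended where vaccine goes only to high-risk recipients. A discrepancy at such a site may therefore be genuine. That is true, and it is a reason to want a comparator without an error of its own in the same direction.

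**Conclusion.** The mismatch is real in the text. Cases and NVT controls must be eligible for vaccination; comparators 1a and 1b need not be. At sites where eligibility follows risk group, crude hospital-control VE is biased downward whenever non-eligible people are vaccinated less often than eligible people. This can make a valid NVT-based VE look too high. Under the stated assumptions (true VE 60%, coverage 50% and 5%), crude VE is about 30% to -34% as the eligible share of comparators goes from 70% to 40%. The eligible share and both coverages are not in the documents, so the size is illustrative; the direction is not sensitive to them.

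The point has limits. It concerns crude estimates, is negligible where everyone aged 65 or over is eligible, and is largely removed by stratifying on eligibility. It does not show that the validation necessarily discredits the NVT-based result. Nor does it extend to the screening method, as might be inferred: that option already uses coverage by age and risk group, and its formula applies only where the coverage represents the same population as the cases. This is a correction worth making in a generic protocol that sites will adapt.

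**What to change.** Add to Appendix 1 that comparators in 1a and 1b must meet the site's eligibility definition under 4.3 and 4.5.4 at the date of admission, or that the comparison is stratified on eligibility or risk condition. Where eligibility cannot be established at a risk-group-only site, 1a and 1b should not be used to judge the NVT controls. Make clear that 1b selects on the reason for admission and does not exclude people who have a risk condition, and point 1a to Table 2 for the pneumococcal codes. The screening method needs no change.

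The risk-condition flags in Table 3 are collected for IPD cases, so they will not serve for other admissions. For hospital comparators, the ICD codes in Table 4 (underlying conditions) would be taken from the discharge register that Appendix 1 already proposes to link. The cost is a sentence or two of text, some extra linkage and coding work, and fewer hospital controls at risk-group sites. Conditions without specific codes, such as institutional residence, would remain imperfectly captured.

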4.8 Power and sample size and calculation

a) Power calculation

According to the number of cases and controls (i.e. VT-IPD cases and NVT-IPD controls, respectively) collected in the IPD surveillance system, we can calculate the power to detect a given vaccine effectiveness (i.e. 1-odds ratio for vaccination). In order to calculate the power, the following parameters should be taken into account:

- the vaccination coverage in the site;
- number of cases, i.e. VT-IPD;
- number of controls, i.e. NVT-IPD;
- predicted vaccine effectiveness depending on the outcome and exposure;
- a significance level of 5%.

For example, in case of o sample size of 100 VT-IPD cases and 300 NVT-IPD controls, the power will vary according to the vaccination coverage and predicted vaccination effectiveness (Figure 1)

[figure not shown]

Figure 1. Power calculation for different vaccination coverage (VC), vaccine effectiveness, for a sample size of 100 VT-IPD and 300 NVT-IPD

b) Sample size calculation

In case not sufficient number of IPD cases are collected by the surveillance system in a given period of time, the sample size should be calculated in order to reach the desired power and precision of VE estimate. To calculate the sample size, the following parameters should be taken into account:

- a significance level of 5%;
- a power of 80%;
- a precision of 20% around the point VE estimate;
- the vaccination coverage available in the site;
- a vaccine effectiveness of 20%-90% depending on the outcome and exposure;
- a proportion of PPV23-IPD among the all IPD cases of 0.60 (based on SpIDnet1 data in >64 years 2012-2014).

The calculation should be done according to each outcome considered: primary outcome (IPD of vaccine serotypes) and secondary outcomes (specific vaccine serotypes/vaccine related serotypes, clinical manifestation, IPD antimicrobial non-susceptibility and severe IPD of vaccine serotypes).

Table 4 presents the sample size needed to reach the chosen precision around point estimate.

Table 4. Sample size needed for the for different vaccine coverages and vaccine effectiveness.

Precision	Alpha	Power	Proportion of vaccine type/ all cases	Vaccine coverage in the source population	Detectable VE(1-OR)	Number of cases	Number of controls	Total IPD patients included
0.2	0.05	0.8	0.6	0.1	0.9	346	231	576
0.2	0.05	8.0	0.6	0.1	0.8	509	339	849
0.2	0.05	8.0	0.6	0.1	0.7	717	478	1195
0.2	0.05	8.0	0.6	0.1	0.6	963	642	1605
0.2	0.05	8.0	0.6	0.1	0.5	1246	831	2077

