Vaccine coverage can be measured using different population sub-groups (from now on called reference groups). The best reference group will be the one representing the vaccination coverage in the population giving rise to the cases.

The size of the reference group should be large (> 1000 individuals).

Examples of sources for vaccination coverage include:

- For GPs with computerised medical records, vaccination coverage can be extracted from the GP's database;
- For GPs without computerised medical records, a sample of patients in a defined time period may be selected and influenza vaccination status documented;
- For GPs without computerised medical records, a sample of the population in the catchment area can be selected and interviewed on their influenza vaccination status (telephone, face to face):
 - Vaccination registries;
 - Health insurance claims data;
 - National surveys;
 - Vaccines distributed, vaccines sales in pharmacies.

Analysis

Measure of effect

When looking within populations where the coverage represents the same population as the cases, the VE against each of the outcomes selected (e.g IPD, SpCAP or pneumococcus serotype outcome) can be calculated as 1- odds of vaccination in cases / odds of vaccination in the population, or:

in which PPV is the proportion of the reference group vaccinated (vaccine coverage in the reference group), and PCV the proportion of influenza cases vaccinated.

Ninety five percent confidence intervals will be computed using the Farrington method²⁴.

TECHNICAL DOCUMENT – Protocol on effectiveness of Pneumo vaccines in elderly

²⁴ Farrington CP. Estimation of vaccine effectiveness using the screening method. Int J Epidemiol. 1993 Aug;22(4):742–6.

Stratified analysis

Analysis will be stratified according to the availability of vaccination coverage in the reference group:

- age groups (<75 and >74 years);
- underlying conditions

These analyses could only be performed if appropriate sample size in each stratum could be reached.

Adjusted analysis, Farrington method

Each case is matched to the coverage from the population that best matches that case according to key confounding variables such as age, chronic conditions and time period. The analysis is then performed as a logistic regression with an offset as the logit of the matched coverage²⁵.

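### Appendix 1 treats screening-method coverage as known even when it is estimated from a sample of just over 1000, so the adjusted 95% CI is too narrow once cases number in the hundreds (minor)

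*Protocol*

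**What the plan says.** Appendix 1 lists control groups that could be used to validate the indirect cohort result. One is the screening method, which compares vaccination among cases with coverage in a reference population. VE is defined as "1- odds of vaccination in cases / odds of vaccination in the population".

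On the coverage source the appendix sets one size rule: "The size of the reference group should be large (> 1000 individuals". Some of the listed sources are samples. For practices without computerised records, "a sample of patients in a defined time period may be selected", or "a sample of the population in the catchment area can be selected and interviewed". National surveys are listed as well. So are computerised practice databases, vaccination registries, claims data and distribution or sales figures.

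On the interval, the text under Measure of effect says: "Ninety five percent confidence intervals will be computed using the Farrington method". No variance formula is given there. Under Adjusted analysis, each case is matched to a coverage figure by age, chronic conditions and period, and "The analysis is then performed as a logistic regression with an offset as the logit of the matched coverage". The model equation that follows has logit coverage on the right-hand side with no coefficient and no error term.

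For the stratified analysis the appendix adds: "These analyses could only be performed if appropriate sample size in each stratum could be reached". It gives no number.

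**The concern.** An offset is a fixed constant. If the coverage behind it was estimated from n people, its logit has sampling variance of about 1/(n p q). The regression does not see this variance, and the reported interval reflects only the error in the cases.

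With few cases the omission hardly shows, because case error dominates. With hundreds or thousands of cases, a reference sample near 1000 contributes a material share of the total error. The rule of more than 1000 is absolute and is not tied to the number of cases, so it does not protect against this. At stake is an overstated precision for the screening VE, in a generic protocol that sites are invited to adapt.

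**Working it through.** **Inputs.** Reference size at the floor (Appendix 1). Vaccine coverage p0, VE and number of vaccine-type (VT) cases n1 from Table 4 (section 4.8). OR = 1 - VE. Vaccination proportion in cases p1 = OR·p0 / (1 - p0 + OR·p0). Simple random sampling of the reference group is assumed.

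**Table 4 first.** Its case numbers follow from

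n1 = [1/(p1 q1) + 1.5/(p0 q0)] / [ln((OR + 0.2)/OR)/1.96]².

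For coverage 0.3 and VE 0.6: p1 = 0.12/0.82 = 0.1463; the numerator is 8.00 + 7.14 = 15.15; the denominator is (0.4055/1.96)² = 0.0428; n1 = 353.9, against 354 in the table. In all, 31 of 32 rows reproduce. The exception is coverage 0.5 with VE 0.2: the table prints 891 cases, the same as its 0.7/0.2 row, where the formula gives 775.

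**Variance left out.** V_case = 1/(n1 p1 q1) and V_ref = 1/(n p0 q0). The offset interval uses V_case alone, so its actual coverage is about 2Φ(1.96/√(1 + V_ref/V_case)) - 1. With n = 1000:

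- Coverage 0.3, VE 0.6, 354 cases: V_case = 0.0226, V_ref = 0.0048, ratio 0.21. The true SE is 10% larger than reported; the interval covers 92.5%.
- Coverage 0.3, VE 0.2, 957 cases: V_case = 0.0055, V_ref = 0.0048, ratio 0.87. The SE is 37% larger; coverage 84.9%.
- Coverage 0.1, VE 0.2, 2315 cases: V_case = 0.0058, V_ref = 0.0111, ratio 1.93. The SE is 71% larger; coverage 74.8%.

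**Exact check.** Enumeration over both binomial counts, with a reference of 1001 people and Table 4 case numbers, gives this actual coverage (%) of the nominal 95% offset interval:

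| Vaccine coverage | VE 60% | VE 50% | VE 40% | VE 30% | VE 20% |
|---|---|---|---|---|---|
| 10% | 89.9 | 86.9 | 83.2 | 79.2 | 74.9 |
| 30% | 92.6 | 91.2 | 89.4 | 87.3 | 84.9 |
| 50% | 92.7 | 91.3 | 89.7 | 87.9 | 84.7 |
| 70% | 91.3 | 89.7 | 87.8 | 85.9 | 83.8 |

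With 775 cases instead of 891, the 50%/20% cell would be about 86%.

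**Is the omitted term the cause?** If coverage is truly known, the same interval covers 94.7-95.6% in these cells. Adding the reference variance at 1001 people restores 95.0-95.2%.

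**Where the effect fades.** With 100 cases and VE 20-60%, exact coverage is 93.8-95.8%. With Table 4 case numbers at VE 80-90% it is about 94-96%. With a reference of 10,000, the VE 20-60% cells cover 92.7-94.8%; with 100,000, 94.8-95.0%.

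**The case against.** Most of the case against this point concerns size and scope, and much of it stands.

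- **The case numbers are borrowed.** Table 4 sizes the indirect cohort, and the Protocol states no screening sample size. Its own power example uses 100 VT cases, where the loss is about one point.
- **The floor is a minimum, and sampling is only one option.** A site using a registry or a very large database has no practical problem.
- **The crude interval cannot be checked.** Only the method's name is given. That the crude interval also omits the reference variance may be inferred but is not shown; the point rests on the offset wording of the adjusted model.
- **Stratum size is mentioned.** The sentence on appropriate stratum size is a partial safeguard for the stratified analysis. It sets no number and does not correct the variance.
- **The analysis is optional.** No primary or secondary VE estimate depends on it.

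Three stronger readings are tempting but unsupported. First, a reader might take 75% as typical. It is one cell. Section 1.1 cites a range of 40-70% for PPSV23 effectiveness; at those VE values and vaccine coverage 30-70%, the interval covers about 88-94%. Second, a reader might infer that reference error generally equals case error. At n = 1000 it reaches case error in only 3 of 32 Table 4 rows, all at coverage 10% with VE 20-40%. Third, a reader might infer that the narrow interval will make sound controls look invalid. Both estimates use the same VT cases, so case error cancels in their difference, and the Protocol sets no rule for declaring disagreement. If non-overlap of the two intervals were the rule, chance non-overlap would be about 0.6% in the worst cell and at most 0.14% at coverage 30-70%. The false-alarm harm is not shown.

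**Conclusion.** The point holds in a limited form and is minor. As written, the adjusted screening interval treats coverage as error-free while allowing it to come from a sample of just over 1000, and nothing in the appendix carries that sampling error into the interval. With a sample near the floor and cases in the hundreds or more, the interval is too narrow.

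The size depends on three assumptions: a sampled reference at the floor, simple random sampling, and Table 4 case numbers. Under them, actual coverage at vaccine coverage 30-70% is about 88-93% for VE 40-60% and 84-88% for VE 20-30%. At vaccine coverage 10% it is 83-90% for VE 40-60%, 79% at VE 30% and 75% at VE 20%. Clustering of a sample by practice would make it worse; fewer cases or a larger coverage source would make it better.

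**What to change.** State in Appendix 1 that, where coverage is estimated from a sample, its variance enters the interval. Any of three routes would do: add 1/(n p q) for each matched stratum; bootstrap the reference sample; or analyse the sampled people as controls in a logistic regression. Keep the plain offset interval for full registries or very large databases.

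Replace the absolute size rule by a condition for using the plain offset, relative to the number of cases in each stratum. For example, to keep actual coverage at 94% or more, V_ref/V_case must not exceed (1.96/1.881)² - 1 = 0.086, so n must be at least n1 p1 q1 / (0.086 p0 q0). With Table 4 case numbers that is about 2,450 people at coverage 0.3 and VE 0.6, about 10,080 at 0.3 and 0.2, and about 22,400 at 0.1 and 0.2. This is not a demand to recruit more people: a site below the threshold simply uses the interval with the added variance.

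The cost is a few lines of code and wider intervals.
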